Endocrine Toxicity	
 Monitor subject for signs and symptoms of endocrinopathies. Non-specific symptoms include headache, fatigue, behavior changes, changed mental status, vertigo, abdominal pain, unusual bowel habits, hypotension and weakness. Severe mass effect symptoms (severe headache, any visual disturbances) or severe hypoadrenalinism (hypotension, severe electrolyte disturbances) are observed with hypophysitis (observed with anti-CTLA4 therapy; very rare with PD-1/L1 inhibitor therapy). Perform magnetic resonance imaging (MRI) to visualize the pituitary gland and rule out any alternative etiology (e.g., disease progression including brain metastases, infection). Consult endocrinologist. Evaluate thyroid function (thyroid stimulating hormone [TSH], free thyroxine [T]3, free T4) and other relevant endocrine labs (e.g., blood glucose, cortisol, sex hormones) depending on suspected endocrinopathy. Falling TSH across 2 measurements with normal or lowered T4 may also suggest pituitary dysfunction and weekly cortisol measurements (9 am cortisol) should be performed. Iodine from CT scans may impact thyroid function tests (TFTs). If a subject has an AE that is thought to be possibly of autoimmune nature (e.g., thyroiditis, pancreatitis, hypophysitis, diabetes insipidus), the investigator should send a blood sample for appropriate autoimmune antibody testing (e.g., anti-thyroid antibodies for thyroid dysfunction, C-peptide and antibodies against glutamic acid decarboxylase and islet cell antibodies should be measured to distinguish between type 1 and 2 diabetes mellitus [DM]). 	

Adverse Event	Endocrine Toxicity		
	Severity	Management	
Hypothyroidism	Grade 1 or 2	
 Continue IP 	
	Grade 3 or 4	
 Hold IP for \geq Grade 3 and consider restarting when symptoms under control. Check anti-TSH receptor antibodies, anti-thyroid peroxidase (TPO) antibody, nuclear medicine thyroid uptake scan. Propranolol or atenolol for symptoms; consider thionamide (carbimazole, methimazole, propylthiouracil [PTU]) if anti-TSH receptor antibody positive. Consider hospitalization and initiate prednisone 0.5–2 mg/kg or equivalent, with gradual taper for painful thyroiditis, severe symptoms or thyroid storm. Introduce thyroid replacement if patient develops hypothyroidism. 	

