Hyperthyroidism (differential diagnosis includes thyroiditis, Grave's disease)	Grade 1 or 2	
 Continue IP 	
	Grade 3 or 4	
 Hold IP for \geq Grade 3 and consider restarting when symptoms under control. Check anti-TSH receptor antibodies, anti-TPO antibody, nuclear medicine thyroid uptake scan. Propranolol or atenolol for symptoms; consider thionamide (carbimazole, methimazole, PTU) if anti-TSH receptor antibody positive. Consider hospitalization and initiate prednisone 0.5–2 mg/kg or equivalent, with gradual taper for painful thyroiditis, severe symptoms or thyroid storm. Introduce thyroid replacement if patient develops hypothyroidism. 	
Hypophysitis	Grade 1	
 Continue IP. 	
	Grade 2 or greater	
 Hold IP for any \geq Grade 2. Treatment consisting of hormone replacement therapy for adrenal insufficiency, central hypothyroidism, central hypogonadism should be instituted immediately. For life threatening symptoms (e.g., adrenal crisis, severe headache, visual field defect): hospitalize and treat with prednisone 1 mg/kg/day or equivalent or higher doses of methylprednisolone, followed by gradual taper. Manage adrenal crisis per standard guidelines. Replace thyroid hormone after corticosteroids have been initiated. 	
Adrenal Insufficiency	Grade 1	
 Continue IP. 	
	Grade 2 or greater	
 Hold until subject is stabilized on replacement hormone therapy prednisone or hydrocortisone as per standard practice. May require mineralocorticoid replacement. Titrate as symptoms dictate. With Grade 2-4, administer stress dose corticosteroids at presentation with gradual taper down to maintenance. 	
Diabetes Mellitus (Type 1 or Type 2)	Note	Clinical Signs	Management
	Even subjects with Type 2 Diabetes mellitus (DM) may develop ketoacidosis, an infrequent event	DM with diabetic ketoacidosis DM without ketoacidosis	
 Hold IP; hospitalize and initiate treatment per standard guidelines. Once the subject has been regulated with insulin substitution, consider restarting IP 
 Hold IP for hyperglycemia \geq Grade 3 Once the subject has been regulated with insulin substitution, consider restarting IP

Adverse Event	General Guidance for Ocular Toxicity			

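### The Grade 3–4 hypothyroidism row of the irAE guidance carries the hyperthyroidism treatment text and should be corrected; its hold/restart rule can stay.

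*Protocol*

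**What the plan says.** The Endocrine Toxicity table in Protocol Section 3.5.2 has separate rows for hypothyroidism and hyperthyroidism. For hypothyroidism at Grade 1 or 2, the only instruction is to continue the drug. At Grade 3 or 4 the cell has five sentences:

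1. Hold the drug at Grade 3 or higher "and consider restarting when symptoms under control".
2. Test for two thyroid antibodies and obtain a nuclear medicine uptake scan.
3. "Propranolol or atenolol for symptoms; consider thionamide (carbimazole, methimazole, propylthiouracil [PTU]) if anti-TSH receptor antibody positive".
4. Consider admission and prednisone, "with gradual taper for painful thyroiditis, severe symptoms or thyroid storm".
5. "Introduce thyroid replacement if patient develops hypothyroidism".

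The Grade 3 or 4 hyperthyroidism cell follows the same sequence. Its third sentence reads: "Propranolol or atenolol for symptoms; consider thionamide (carbimazole, methimazole, PTU) if anti-TSH receptor antibody positive".

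The neighbouring hormone-deficiency rows are built around replacement. Hypophysitis says "Treatment consisting of hormone replacement therapy for adrenal insufficiency, central hypothyroidism, central hypogonadism should be instituted immediately" and then "Replace thyroid hormone after corticosteroids have been initiated". Adrenal insufficiency says "Hold until subject is stabilized on replacement hormone therapy".

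**The concern.** Sentences 3 and 4 treat thyroid hormone excess. Thionamides reduce thyroid output, and thyroid storm is a state of excess. Sentence 5 makes replacement depend on the subject developing hypothyroidism, which only makes sense for someone who starts out hyperthyroid. Under a hypothyroidism heading, a site that looks up the treatment finds the work-up and drugs for the opposite disorder. It finds no direct instruction to give the treatment that is needed.

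The event is foreseen. The schedules of assessments call for TSH and free T4 at screening and repeatedly on treatment. Section 3.2.6 exempts Grade 3 hypothyroidism from being a DLT when treatment can control it. What is at stake is the care of an individual subject in a first-in-human trial run in several countries. The statistical design is not affected.

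**Working it through.** No figure in the plan needs reproducing. The check sets the two Grade 3 or 4 cells side by side, counting words as strings separated by spaces.

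| Sentence | Content | Hypothyroidism row (words) | Hyperthyroidism row (words) | Difference |
|---|---|---|---|---|
| 1 | Hold/restart | 13 | 13 | none |
| 2 | Antibodies, uptake scan | 13 | 11 | TPO spelled out: 3 words against 1 |
| 3 | Beta-blocker, thionamide | 16 | 15 | PTU spelled out: 2 words against 1 |
| 4 | Admission, prednisone | 20 | 20 | none |
| 5 | Replacement | 7 | 7 | none |
| Total | | 69 | 66 | |

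Non-matching words are 3 + 2 = 5 in the hypothyroidism cell and 1 + 1 = 2 in the hyperthyroidism cell. Matching words are 69 − 5 = 64 and 66 − 2 = 64, so the two counts agree. The cells do not differ in substance.

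Three inferences follow.

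- **Which row the text belongs to.** Sentence 5 settles this from the document alone. A condition that waits for hypothyroidism is meaningful under hyperthyroidism and empty under hypothyroidism. The content of sentences 3 and 4 points the same way.
- **Whether PDF reading could have caused it.** A cell duplicated by the reading program would be identical to its source. Here the abbreviations are spelled out in the first row and shortened in the second, as an author or editor would do. Other tables in the section are visibly damaged, however (for example, the Grade 4 nephrotoxicity text sits under Grade 3), so the source PDF should be checked.
- **What is sound.** Sentence 1 is also identical in both rows, so it cannot be defended as separately written. It stands because it fits hypothyroidism and agrees with the general Grade 3 irAE instruction to hold the drug. It also parallels the diabetes row, which allows a restart once the subject is controlled on insulin.

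By sentence, one can stay (1), three contain text to remove (2, 3 and 4), and one needs its condition removed (5).

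**The case against.** The strongest reply is that little harm could follow. The opening of Section 3.5.2 says the guidance does not bind and that institutional guidelines apply where appropriate. The general endocrine text calls for thyroid function tests and an endocrinology consult. The doubtful instructions are also gated: a thionamide is only to be considered, and only with a positive receptor antibody; beta-blockers are for symptoms; and a hypothyroid subject already meets the condition for replacement. Read literally, the row still leads to replacement. On this view it is an editorial slip.

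Much of that stands, and it limits the severity. It is also true that the cross-references from elsewhere reach only part of the cell. Section 3.7, on resuming treatment, leads to the hold/restart sentence, which is not in dispute. Section 3.4.2 reaches only the steroid sentence. But the cell is itself treatment guidance in the protocol's toxicity section and needs no cross-reference to be read and followed. The safeguards lower the chance that a site acts on it; they do not make the text right. The steroid trigger for severe symptoms could plausibly be met by a Grade 3 or 4 hypothyroid subject.

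A second objection is useful. An unconditional replacement instruction could mislead when the cause is pituitary, because the hypophysitis row requires corticosteroids first. The corrected cell should say so.

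**Conclusion.** The text is wrong as written and should be fixed. The error is confined to one five-sentence cell, in which 64 of 69 words match the hyperthyroidism cell. That count measures duplication of text; it does not measure risk. The documents give no expected rate of Grade 3 or 4 hypothyroidism, so no number of affected subjects can be stated. No effect on DLT status, the MTD, sample size or any analysis is claimed.

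The conclusion assumes that the extracted table matches the source PDF, which the differing abbreviations support. The direction of copying is inferred from the clinical content and from the closing conditional sentence.

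One adjacent feature is noted but forms no part of this finding. For Grade 4, the hold/restart rule is more lenient than the general irAE default of permanent discontinuation. That default is worded as a general approach, and the hyperthyroidism row has the same feature.

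**What to change.** Check the source PDF first. Then, in the Grade 3 or 4 hypothyroidism cell:

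1. Keep the hold/restart sentence.
2. Delete the uptake scan, the beta-blocker and thionamide sentence, and the thyroid-storm steroid text. Antibody testing is already covered by the general endocrine text above the table.
3. Replace the last sentence with an unconditional instruction to start thyroid hormone replacement with endocrinology input, in line with the hypophysitis and adrenal insufficiency rows.
4. Leave the hypophysitis rule unchanged (thyroid hormone after corticosteroids) as the rule for central hypothyroidism, and cross-refer to it within this cell.

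The sponsor's medical lead should set the final wording, and could decide at the same time whether the Grade 1 or 2 entry also needs a line on replacement. The cost is one table cell at the next protocol amendment and a short clarification letter to sites in the meantime. Design, sample size and analysis are unchanged.

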3.5.3 Management of Non-irAEs

Severity	Dose Modification	Toxicity Management
Any Grade	Note: Dose modifications are not required for AEs not deemed to be related to SL-279252 (i.e., events due to underlying disease) or for laboratory abnormalities not deemed to be clinically significant.	
 Treat accordingly, as per institutional standard
Grade 1	No dose modifications	
 Treat accordingly, as per institutional standard
Grade 2	Consider holding SL-279252 until resolution to \leq Grade 1 or baseline.	
 Treat accordingly, as per institutional standard
Grade 3	Hold SL-279252 until resolution to \leq Grade 1 or baseline. For AEs that downgrade to \leq Grade 2 within 7 days or resolve to \leq Grade 1 or baseline within 14 days, resume SL-279252 administration. Otherwise, discontinue SL-279252. (Note: For Grade 3 labs, decision to hold should be based on accompanying clinical signs/symptoms, the Investigator's clinical judgment, and consultation with the Sponsor).	
 Treat accordingly, as per institutional standard
Grade 4	Discontinue SL-279252 (Note: For Grade 4 labs, decision to discontinue should be based on accompanying clinical signs/symptoms, the Investigator's clinical judgment, and consultation with the Sponsor).	
 Treat accordingly, as per institutional standard

(Reference: American Society of Clinical Oncology Educational Book 2015 "Managing Immune Checkpoint Blocking Antibody Side Effects" by Michael Postow MD.)

3.6 Discontinuation of Investigational Product

SL-279252 should be discontinued by the investigator when a participant meets one of the conditions requiring discontinuation outlined in Section 3.5. The investigator may, however, elect to discontinue SL-279252 for an AE, laboratory abnormality, or intercurrent illness which, in the judgment of the investigator, presents substantial clinical risk to the subject with continued dosing of the IP. If SL-279252 is permanently discontinued for reasons other than progressive disease or withdrawal of consent, the participant will remain in the study to be evaluated for disease progression, and survival. See the SOA in Section 6 for data to be collected at the time of discontinuation of SL-279252.

3.7 Criteria to Resume Treatment

A participant may resume IP per the guidance outlined in Section 3.5. If the criteria to resume treatment are met, the subject should restart treatment at the next scheduled time point per protocol.

3.8 Participant Discontinuation/Withdrawals from Study

- A participant may withdraw from the study at any time at his/her own request; or may be withdrawn at any time at the discretion of the investigator for safety, behavioral, compliance, or administrative reasons. This is expected to be uncommon.
- At the time of discontinuing from the study, an early discontinuation visit should be conducted, as shown in the SOA in Section 6. See SOA for data to be collected at the time of study discontinuation and follow-up and for any further evaluations that need to be completed. The participant will be permanently discontinued both from the IP and from the study at that time. Every effort must be made to continue follow-up of participants for protocol-specified safety follow-up procedures to capture AEs, SAEs, and unanticipated problems (UPs).
- If the participant withdraws consent for disclosure of future information, the Sponsor may retain and continue to use any data collected before such a withdrawal of consent.
- If a participant withdraws from the study, he/she may request destruction of any samples taken and not tested, and the investigator must document this in the site study records.

3.9 Lost to Follow-up

- A participant will be considered lost to follow-up if he or she repeatedly fails to return for scheduled visits and is unable to be contacted by the study site.
- The following actions must be taken if a participant fails to return to the clinic for a required study visit:
 - The site must attempt to contact the participant and reschedule the missed visit as soon as possible and counsel the participant on the importance of maintaining the assigned visit schedule and ascertain whether the participant wishes to and/or should continue in the study.

- Before a participant is deemed lost to follow up, the investigator or designee must make every effort to regain contact with the participant (where possible, 3 telephone calls and, if necessary, a certified letter sent to the participant's last known mailing address or local equivalent methods). These contact attempts should be documented in the participant's medical record.
- Should the participant continue to be unreachable, he/she will be considered as lost to follow up and withdrawn from the study.

3.10 Premature Termination or Suspension of Study

The Sponsor reserves the right to close the study site or terminate the study at any time for any reason. Written notification, documenting the reason for study suspension or termination, will be provided by the Sponsor to investigators, the Food and Drug Administration (FDA), Health Canada, European Medicines Agency and other regulatory authorities. If the study is prematurely terminated or suspended, the investigator will promptly inform the Institutional Review Board/Institutional Ethics Board (IRB/IEC) and will provide the reason(s) for the termination or suspension. Study sites will be closed upon study completion. A study site is considered closed when all required documents and study supplies have been collected or destroyed and a study-site closure visit has been performed.

The investigator may initiate study-site closure at any time, provided there is reasonable cause and sufficient notice is given in advance of the intended termination.

Reasons for the early closure of a study site by the Sponsor or investigator may include but are not limited to:

- Failure of the investigator to comply with the protocol, the requirements of the IRB/IEC or local health authorities, the Sponsor's procedures, or GCP guidelines
- Inadequate recruitment of participants by the investigator
- Discontinuation of further development of the IP
- Determination of unexpected, significant, or unacceptable risk to participants

3.11 Duration of Treatment

In the absence of treatment delays due to AE(s), treatment may continue until one of the following criteria applies:

- Disease progression per iRECIST or RECIL 2017; **NOTE:** See Section 8.3 for criteria allowing for continuing treatment past initial progression.
- Death
- Intercurrent illness that prevents further administration of treatment
- Unacceptable AE(s)
- Participant decides to withdraw from the study
- General or specific changes in the participant's condition render the participant unacceptable for further treatment in the judgment of the investigator
- Participant non-compliance

- Pregnancy
- Termination of the study by Sponsor

All women of childbearing potential should be instructed to contact the investigator immediately if they suspect they might be pregnant (e.g., missed or late menstrual period) at any time during study participation. The investigator should immediately notify PrimeVigilance upon knowledge of pregnancy (Section 7.6).

The investigator may consider discontinuing IP after agreement with the Sponsor if a subject has achieved maximal clinical benefit (a durable CR or PR or SD of >6 months). The subject will be followed until confirmed disease progression as per protocol. Subject may be eligible for treatment past progression if they meet criteria as outlined in Section 8.3.

Impact of ADA on clinical efficacy (non-response or loss of response to the IP) and safety (product specific immunogenicity risk) will be evaluated and reported on an on-going basis once a validated ADA assay becomes available. If a subject develops ADA, the Sponsor and investigator may take into consideration these factors in assessing the duration of the therapy.

3.12 Duration of Follow-Up

Safety follow-up is at least 90 days after the last dose of SL-279252 (Section 6). Subjects who are withdrawn from study for unacceptable AE(s) will be followed until resolution or stabilization of the AE. Participants who permanently discontinue IP for reasons other than progression will continue with disease assessments until progression (per iRECIST or RECIL) or start of another anti-cancer therapy. Participants who discontinue IP for any reason other than withdrawal of consent will be followed for survival.

3.13 End-of Study Definition

The end-of-study is defined as the point of final data capture (the point at which all required data has been collected to answer the research questions in the protocol). At least 3 months of follow up from the last subject enrolled is required.

4. STUDY POPULATION

4.1 Trial Participants

Participants with advanced stage solid tumors or lymphomas of the histologic types described below may be considered for enrollment in the study if they meet all the eligibility criteria stated in Sections 4.2 and 4.3. Prospective approval of protocol deviations to recruitment and enrollment criteria, also known as protocol waivers or exemptions, is not permitted.

4.2 Participant Inclusion Criteria

Participants are eligible to be included in the study only if all the following criteria apply.

1. Subject has voluntarily agreed to participate by giving written informed consent in accordance with ICH/GCP guidelines and applicable local regulations.

2. Subject has a histologically confirmed diagnosis of one of the following unresectable locally advanced or metastatic malignancies: melanoma, non-small cell lung cancer (squamous, adeno, or adeno-squamous), urothelial cancer, squamous cell carcinoma of the head and neck, squamous cell cervical cancer, gastric or gastro-esophageal junction adenocarcinoma, squamous cell carcinoma of the anal canal, squamous cell carcinoma of the skin, renal cell cancer, Hodgkin's lymphoma, and microsatellite instability high (MSI-H) or mismatch repair deficient (MMRD) solid tumors excluding CNS malignancies. MSI and MMRD testing results as per institution is acceptable.
 - **Head and neck cancers**: Subjects must have primary tumor locations in the oropharynx, oral cavity, hypopharynx, or larynx. Primary tumor sites of nasopharynx, maxillary sinus, paranasal, and unknown primary are excluded.
 - **Non-small cell lung cancers**: Subjects with a known EGFR sensitizing (activating) mutation or an ALK fusion are excluded.
 - **Melanoma**: Subjects with a diagnosis of uveal or ocular melanoma are excluded.
3. Eligible subjects must have tumors expressing PD-L1 $\geq 1\%$ by tumor proportion score (TPS) or combined proportion score (CPS) as determined by a local laboratory.
 - This criteria does not apply to subjects with a diagnosis of melanoma, renal cell carcinoma, Hodgkin's lymphoma and microsatellite instability high (MSI-H) or mismatch repair deficient (MMRD) solid tumors.
4. Subject must have received, been intolerant to, or is ineligible for standard therapy (per local guidelines and approvals) or have a malignancy for which there is no approved therapy considered standard of care.
5. Age 18 years and older.
6. Has an Eastern Cooperative Oncology Group Performance Status (ECOG PS) of 0 or 1.
7. Has measurable disease by iRECIST (solid tumors) or RECIL 2017 (lymphoma). Refer to Appendix Sections [16.6](#) and [16.7](#) for details on criteria of measurable disease.
8. Has life expectancy of greater than 12 weeks.
9. Laboratory values must meet the following criteria.

Laboratory parameter	Threshold value
Absolute lymphocyte count (ALC)	$\geq 0.8 \times 10^9/\text{liter (L)}$
Absolute neutrophil count (ANC)	$\geq 1.5 \times 10^9/\text{L}$ without growth factor support

Platelet count	$\geq 50 \times 10^9/L$
Hemoglobin (Hgb)	$> 9.0 \text{ g/dL}$ with no blood transfusions for at least 5 days prior to D1 of IP.
Creatinine clearance (CrCl)	$\geq 30 \text{ milliliter (mL)/min}$ (using modified Cockcroft-Gault formula; Appendix Section 16.5)
ALT/AST	$\leq 3 \times \text{ULN}$
Total bilirubin	$\leq 1.5 \times \text{ULN}$; subjects with isolated indirect hyperbilirubinemia are permitted if direct bilirubin ratio is $<35\%$ and total bilirubin is $\leq 3.0 \times \text{ULN}$
Left ventricular ejection fraction (LVEF) by ECHO	\geq Lower limit of normal (LLN) per institutional threshold If LLN is not defined for a given institution, then ejection fraction must be $\geq 50\%$

10. Females of child bearing potential (FCBP) must have a negative serum or urine pregnancy test within 72 hours of D1 of IP. **NOTE:** FCBP unless they are surgically sterile (i.e., have undergone a complete hysterectomy, bilateral tubal ligation/occlusion, bilateral oophorectomy or bilateral salpingectomy), have a congenital or acquired condition that prevents childbearing or are naturally postmenopausal for at least 12 consecutive months (see Appendix Section 16.2 for additional details). Documentation of postmenopausal status must be provided. FCBP should use an acceptable method of contraception (see Appendix Section 16.2) to avoid pregnancy during treatment and for 30 days (which exceeds 5 half-lives) after the last dose of IP. FCBP must start using acceptable contraception at least 14 days prior to D1 of IP.
11. Male subjects with female partners must have azoospermia from a prior vasectomy or underlying medical condition or agree to use an acceptable method of contraception during treatment and for 30 days (which exceeds 5 half-lives) after last dose of SL-279252 (see Appendix 16.2). Male subjects of reproductive potential must start using acceptable contraception at least 14 days prior to D1 of treatment with SL-279252 as per Appendix Section 16.2.
12. All AEs resulting from prior anti-cancer immunotherapy have resolved (**NOTE:** exceptions include alopecia, vitiligo, and endocrinopathies adequately treated with hormone replacement).
 - Subjects that were discontinued from prior PD-1/L1 therapy due to immune-related adverse events are not eligible
13. Recovery from toxicities from prior anti-cancer treatments including surgery, radiotherapy, chemotherapy or any other anti-cancer therapy to baseline or \leq Grade 1. (**NOTE:** Low-grade toxicities (e.g., alopecia, \leq Grade 2 lymphopenia, \leq Grade 2 hypomagnesemia, \leq Grade 2 neuropathy) may be allowed at the discretion of the investigator if considered clinically insignificant. Please consult the Sponsor Medical Monitor to discuss these cases).

